- B. H_1^{10} : 50 μ g mRNA-1273.214, as a second booster dose, against ancestral SARS-CoV-2 is non-inferior to the booster dose of (50 μ g) mRNA-1273 against ancestral SARS-CoV-2 based on the difference in SRR at Day 91 with a non-inferiority margin of 10%.

If the lower bound of the 97.5% CI of the SRR difference (50 μ g mRNA-1273.214 against ancestral SARS-CoV-2— 50 μ g mRNA-1273 against ancestral SARS-CoV-2) is >-10% at Day 29 or Day 91, then the key secondary objective will be considered met.

In the event that an early assessment of the 1273.214 data is needed due to public health concerns, a two-staged approach might be used. Specifically, a subset of participants' (ie, 50 first enrolled participants) serum samples will first be tested against ancestral SARS-CoV-2 and variants of concern. For the Day 29 and Day 91 immunogenicity analyses, all participants' immune data will be used in the formal interim analysis to evaluate the primary immunogenicity objective.

Part H:

The primary immunogenicity objective will be assessed in the per-protocol immunogenicity, SARS-CoV-2 negative set.

The analyses methods described in Part F Cohort 1 will be used for Part H.

The primary immunogenicity objective is considered met if non-inferiority against Omicron BA.4/5 and ancestral SARS-CoV-2 D614G based on GMR and SRR difference at Day 29 is demonstrated.

Non-inferiority against Omicron BA.4/5:

- The lower bound of the 95% CI of the GMT ratio between mRNA-1273.222 against Omicron BA.4/5 at Day 29 as compared to 50 μ g mRNA-1273 against BA.4/5 at Day 29 is > 0.667 based on the non-inferiority margin of 1.5.
- The lower bound of the 95% CI of the SRR difference (50 μ g mRNA-1273.222 against Omicron BA.4/5 at Day 29— 50 μ g mRNA-1273 against BA.4/5 at Day 29) is >-5%.

Non-inferiority against ancestral SARS-CoV-2 D614G:

- The lower bound of the 95% CI of the GMT ratio between mRNA-1273.222 against ancestral SARS-CoV-2 D614G at Day 29 as compared to 50 μ g mRNA-1273 against ancestral SARS-CoV-2 D614G at Day 29 is > 0.667 based on the non-inferiority margin of 1.5.
- The lower bound of the 95% CI of the SRR difference (50 μ g mRNA-1273.222 against ancestral SARS-CoV-2 D614G at Day 29— 50 μ g mRNA-1273 against ancestral SARS-CoV-2 D614G at Day 29) is >-10%.

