If non-inferiority is demonstrated based on GMT ratio and SRR difference against Omicron BA. 4/5 and ancestral SARS-CoV-2 D614G then the lower bound of 95% CI of the GMT ratio will be compared to 1, and if it is higher than 1 then superiority will also be demonstrated.

Part J:

No formal hypothesis testing will be performed for Part J and all safety and immunogenicity analyses will be descriptive. The primary immunogenicity objective will be assessed using the Per-Protocol Set for Immunogenicity. Comparisons on immunogenicity response between the mRNA-1273.815 and mRNA-1273.231 treatment arms may be performed.

Immunogenicity endpoints applicable to all study parts:

SARS-CoV-2-specific bAb and nAb are assessed at multiple timepoints in each part of this study.

For each of the antibodies of interest, eg, levels of SARS-CoV-2-specific bAb and SARS-CoV-2-specific nAb, the GMT or level with corresponding 95% CI at each time point, and GMFR of post-baseline/baseline titers or levels with corresponding 95% CI at each post-baseline time point will be provided for each arm. The 95% CIs will be calculated based on the t-distribution of the log-transformed values then back-transformed to the original scale for presentation. The following descriptive statistics will also be provided at each time point: number of participants (n), median, minimum, and maximum.

The mixed effect model repeated measure (MMRM) will be used to analyze all postbooster measures for between-booster comparison when applicable, the model will include treatment group, analysis visit, treatment by visit interaction, and adjusting for age groups and prebooster titer levels. An unstructured covariance structure will be used to model the within-participant errors. The GMT will be estimated from the model and its corresponding 95% CI will be provided for each group at each postboost timepoint. The GMR (ratio of GMTs) will be estimated from the model and the corresponding 95% CI will be provided at each postboost timepoint.

The SRR of each arm against ancestral SARS-CoV-2 and variants, defined as the percentage of participants achieving seroresponse against ancestral SARS-CoV-2 and variants respectively, will be provided for each arm with the 95% CI calculated using the Clopper-Pearson method.

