- A. H_1^1 : 50 μ g mRNA-1273.222, as a second booster dose, against Omicron BA.4/5 is non-inferior to the second booster dose of (50 μ g) mRNA-1273 against Omicron BA.4/5 based on the GMT ratio of mRNA-1273.222 against Omicron BA.4/5 at Day 29 compared to mRNA-1273 against Omicron BA.4/5 at Day 29 with a non-inferiority margin of 1.5.
- B. H_1^2 : 50 μ g mRNA-1273.222, as a second booster dose, against Omicron BA.4/5 is non-inferior to the second booster dose of (50 μ g) mRNA-1273 against Omicron BA.4/5 based on the difference in SRR at Day 29 with a non-inferiority margin of 5%.

- C. H_1^3 : 50 μ g mRNA-1273.222, as a second booster dose, against ancestral SARS-CoV-2 D614G is non-inferior to the second booster dose of (50 μ g) mRNA-1273 against ancestral SARS-CoV-2 D614G based on the GMT ratio of mRNA-1273.222 against ancestral SARS-CoV-2 D614G at Day 29 compared to mRNA-1273 against ancestral SARS-CoV-2 D614G at Day 29 with a non-inferiority margin of 1.5.
- D. H_1^4 : 50 μ g mRNA-1273.222, as a second booster dose, against ancestral SARS-CoV-2 D614G is non-inferior to the second booster dose of (50 μ g) mRNA-1273 against ancestral SARS-CoV-2 D614G based on the difference in SRR at Day 29 with a non-inferiority margin of 10%.
- E. H_1^5 : 50 μ g mRNA-1273.222, as a second booster dose, against Omicron BA.4/5 is superior to the second booster dose of (50 μ g) mRNA-1273 against Omicron BA.4/5 based on the GMT ratio of mRNA-1273.222 against Omicron BA.4/5 at Day 29 compared to mRNA-1273 against Omicron BA.4/5 at Day 29.

Part J:

No formal hypothesis testing will be performed for Part J and all safety and immunogenicity analyses will be descriptive.

The primary immunogenicity objective will be assessed using the Per-Protocol Set for Immunogenicity. Comparisons on immunogenicity response between the mRNA-1273.815 and mRNA-1273.231 treatment arms may be performed.

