10.5.2. Amendment 9, 30 Sep 2022

Main Rationale for the Amendment

The main purpose of this amendment is to update the statistical analyses of Part H (vaccine mRNA-1273.222) to include a primary immunogenicity objective of a comparison between the mRNA-1273.222 and mRNA-1273 groups of the antibody response against the ancestral SARS-CoV-2 D614G.

The summary of changes table provided below describes the major changes made to Amendment 9 relative to Amendment 8, including the sections modified and corresponding

rationales. The synopsis of Amendment 9 has been modified to correspond to changes in the body of the protocol. Minor copy edits and administrative updates were made throughout the protocol to align with new content and/or for accuracy.

Section # and Name	Description of Change	Brief Rationale
Title Page, Protocol Approval Page, and Protocol Amendment Summary of Changes	Updated protocol version and date. Added Summary of Changes.	Updated to reflect the new protocol version. Summary of Changes added to be in line with Moderna guidelines for protocol amendments.
Synopsis; Section 2.0: Objectives and Endpoints Part H; Section 8.2: Statistical Hypotheses; Section 8.5.3.2.8: Analysis for the Primary Immunogenicity Objective for Part H	Added evaluation of the neutralizing antibody response elicited by mRNA-1273.222 vs. mRNA-1273 against the ancestral SARS-CoV-2 D614G strain as a co-primary immunogenicity endpoint	Because mRNA-1273.222 is a bivalent vaccine with an antigenic component that also targets the ancestral SARS-CoV-2 D614G strain, a comparison of the antibody responses against the ancestral SARS-CoV-2 between the vaccine groups is now included in the primary immunogenicity objectives as a comparison.
Synopsis; Section 8.0: Statistical Analysis Plan	Revised the seroresponse rate success criteria against BA.4/5 for Part H using a 5% non-inferiority margin.	This was updated based on the SRR data from another Omicron-containing bivalent vaccine, mRNA-1273.214.
Synopsis; Section 8.5.3.2: Analysis for Primary Immunogenicity	Revised the GMR non-inferiority boundary for all study parts, from ≥ 0.67 to > 0.667 .	This is a technical update of the GMR non-inferiority success criterion.
Synopsis; Section 8.0: Statistical Analysis Plan	Added evaluation of seroresponse based on secondary definition to Parts F (Cohort 2), G, and H.	This update will enable use of both seroresponse rate definitions in the data analysis.

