With approximately 375 participants exposed to 50 μ g mRNA-1273.214, there is at least 90% probability in this group to observe 1 participant reporting an AE if the true rate of AEs is 1%.

Part H

The target enrollment is approximately 500 participants for 50 μ g mRNA1273.222. Assuming 40% of participants will be excluded from the PPIS-Neg (due to a SARS-CoV-2 infection pre-booster), with approximately 300 participants in 50 μ g mRNA1273.222 and 260 participants in 50 μ g mRNA-1273 (Part F, Cohort 2-50 μ g mRNA-1273) in the PPIS and SARS-CoV-2 negative, there is approximately 60% power to demonstrate the primary immunogenicity objectives with alpha of 0.05 (2-sided) at Day 29. The assumptions are: the true GMR (mRNA-1273.222 second booster vs. 50 μ g mRNA-1273 second booster) against Omicron BA.4/5 is 1.5, GMR (mRNA-1273.222 second booster vs. mRNA-1273 second booster) against ancestral SARS-CoV-2 D614G is 1, the standard deviation of the log-transformed titer is 1.5, and the non-inferiority margin for GMR is 1.5. The true SRR against Omicron BA.4/5 after mRNA-1273.222 as a second booster dose is 95% (same assumption for 50 μ g mRNA-1273), and non-inferiority margin for SRR difference against Omicron BA.4/5 is 5%. The true SRR against ancestral SARS-CoV-2 D614G after mRNA-1273.222 as a second booster dose is 95% (same assumption for 50 μ g mRNA-1273), and the non-inferiority margin for SRR difference against ancestral SARS-CoV-2 D614G is 10%.

With approximately 500 participants exposed to 50 μ g mRNA-1273.222, there is at least 90% probability in this group to observe 1 participant reporting an AE if the true rate of AEs is 1%.

Part J

The sample size for Part J is not driven by statistical assumptions for formal hypothesis testing. The number of proposed participants is considered sufficient to provide a descriptive summary of the safety and immunogenicity of each treatment arm.

The target enrollment is approximately 100 participants who will be randomized in a 1:1 ratio to receive either mRNA-1273.815 (50 μ g) or mRNA-1273.231 (50 μ g).

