- The lower bound of the 95% CI of the GMT ratio between mRNA1273.222 against Omicron BA.4/5 at Day 29 as compared to 50 μ g mRNA-1273 against Omicron BA.4/5 at Day 29 is > 0.667 based on the non-inferiority margin of 1.5.
- 50 μ g mRNA-1273.222, as a second booster dose, against Omicron BA.4/5 is non-inferior to the second booster dose of (50 μ g) mRNA-1273 against Omicron BA.4/5 based on the difference in SRR at Day 29 based on a non-inferiority boundary, if:
 - The lower bound of the 95% CI of the SRR difference (50 μ g mRNA-1273.222 against Omicron BA.4/5 at Day 29 - 50 μ g mRNA-1273 against Omicron BA.4/5 at Day 29) is $>-5\%$, then the non-inferiority of mRNA-1273.222 against Omicron BA.4/5 compared to that of mRNA-1273 is demonstrated based on a non-inferiority margin of 5%.
 - The lower bound of the 95% CI of the SRR difference (50 μ g mRNA-1273.222 against Omicron BA.4/5 at Day 29 - 50 μ g mRNA-1273 against Omicron BA.4/5 at Day 29) is $>-10\%$ but $\leq-5\%$, then non-inferiority of mRNA-1273.222 against Omicron BA.4/5 compared to that of mRNA-1273 is demonstrated based on a non-inferiority margin of 10%.
- The lower bound of the 95% CI of the GMT ratio between mRNA1273.222 against the ancestral SARS-CoV-2 D614G at Day 29 as compared to 50 μ g mRNA-1273 against the ancestral SARS-CoV-2 D614G at Day 29 is > 0.667 based on the non-inferiority margin of 1.5.
- The lower bound of the 95% CI of the SRR difference (50 μ g mRNA-1273.222 against the ancestral SARS-CoV-2 D614G at Day 29 - 50 μ g mRNA-1273 against ancestral SARS-CoV-2 D614G at Day 29) is $>-10\%$.
- If non-inferiority is demonstrated (against Omicron BA.4/5 and ancestral SARS-CoV-2 D614G based on GMT ratio and SRR difference with a NI margin of 10%), the lower bound of 95% CI of GMT ratio will be compared to 1, if it's greater than 1, then superiority is demonstrated.

Part J

No formal hypothesis testing will be performed for Part J and all safety and immunogenicity analyses will be descriptive.

The primary immunogenicity objective will be assessed using the Per-Protocol Immunogenicity Set. Descriptive comparisons on immunogenicity response between the mRNA-1273.815 and mRNA-1273.231 treatment arms will be performed.

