Summary of major changes in SAP Version 5.0

Section	Brief Description of Changes	Rationale
2.1 (Primary Objectives), 2.2 (Secondary Objectives), 2.3 (Exploratory Objectives)	Added objectives for Part H.	Updated according to protocol amendment 9.
3.1 (Primary Endpoints), 3.2 (Secondary	Added endpoints for Part H.	Updated according to protocol amendment 9.

Endpoints), 3.3 (Exploratory Endpoints)		
4.1 (Overall Study Design), 4.2 (Statistical Hypotheses), 4.3 (Sample Size and Power)	Added details for Part H.	Updated according to protocol amendment 9.
6.4.3 (Primary Analysis of Antibody-Mediated Immunogenicity Endpoints)	Revised the GMR non-inferiority boundary for all study parts, from ≥ 0.67 to > 0.667 .	Updated according to protocol amendment 9.
6.4.3 (Primary Analysis of Antibody-Mediated Immunogenicity Endpoints), 6.4.4 (Secondary Analysis of Antibody-Mediated Immunogenicity Endpoints)	Added analysis for Part H.	Updated according to protocol amendment 9.
6.4.7 Seroresponse	Added evaluation of seroresponse will be based on both definitions for all study parts.	Updated according to protocol amendment 9.

Summary of major changes in SAP Version 6.0

Section	Brief Description of Changes	Rationale
2.1 (Primary Objectives), 2.3 (Exploratory Objectives)	Added objectives for Part J.	Updated according to protocol amendment 10.

3.1 (Primary Endpoints), 3.3 (Exploratory Endpoints)	Added endpoints for Part J.	Updated according to protocol amendment 10.
4.1 (Overall Study Design), 4.2 (Statistical Hypotheses), 4.3 (Sample Size and Power), 4.4 (Randomization)	Added details for Part J.	Updated according to protocol amendment 10.
6.4.3 (Primary Analysis of Antibody-Mediated Immunogenicity Endpoints)	Added details for Part J.	Updated according to protocol amendment 10.
6.5.1.1 (Derivation of SARS-CoV-2 Infection), 6.5.1.2 (Derivation of Asymptomatic SARS- CoV-2 Infection)	Added clarification on derivation. SARS-CoV-2 negative status is required when positive test result is based on serology test post baseline.	Added clarification.
6.6 Interim Analysis	Added information for Part J.	Updated according to protocol amendment 10.
6.8 Final Analysis	Added information for Part J.	Updated according to protocol amendment 10.

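### Part H: the SAP accepts a BA.4/5 seroresponse lower bound above −10%, where the protocol requires one above −5%

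*SAP*

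**What the plan says.** **Protocol.** The Part H hypothesis on BA.4/5 SRR in section 8.2 is "based on the difference in SRR at Day 29 with a non-inferiority margin of 5" (per cent). Sections 8.3 and 8.5.3.1.5 use the same margin. The synopsis, under Immunogenicity Analyses, turns it into a bound: the lower 95% limit of the difference from "mRNA-1273 against BA.4/5 at Day 29) is >-5" (per cent). The synopsis then gates superiority on that result: "If non-inferiority is demonstrated based on GMT ratio and SRR difference against Omicron BA. 4/5 and ancestral SARS-CoV-2 D614G then" the GMT-ratio limit is compared with 1. Within Part H, 10% applies only to SRR against ancestral D614G. The 5% figure was a deliberate change in Amendment 9: "Revised the seroresponse rate success criteria against BA.4/5 for Part H using a 5% non-inferiority margin". Amendment 11, the current version, keeps it.

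**SAP.** Sections 4.2 and 6.4.3 contain the 5% rule and then a further branch for a lower limit above −10% but not above −5%, in which case "then non-inferiority of mRNA-1273.222 against Omicron BA.4/5 compared to that of mRNA-1273 is demonstrated based on a non-inferiority margin of 10" (per cent). In 6.4.3 this stands among the criteria for meeting the primary objective. The superiority step there is conditioned on "SRR difference with a NI margin of 10%), the lower bound of 95% CI of GMT ratio will be compared to 1". The SAP's own power statement in 4.3 nevertheless says "non-inferiority margin for SRR difference against Omicron BA.4/5 is 5" (per cent).

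**Which document governs.** SAP section 1 says the SAP prevails where methods differ, but describes its own modifications as not principal in nature. Protocol section 8 requires a protocol amendment when methods for primary objectives change.

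**The concern.** Any lower limit above −10% passes under the SAP, so its 5% tier decides nothing. The margin for a primary criterion has been doubled in the lower-ranking document, and the precedence clause would make the looser version govern.

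Both tiers are written down and both are read from one confidence interval, so this is not a multiplicity problem, nor a choice made after seeing the interval. The difficulty is that one Day 29 result can fail the Part H primary objective under the protocol and meet it under the SAP. The entry condition for the BA.4/5 superiority claim differs in the same way, and the published power describes only one of the two rules.

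**Working it through.** **Inputs** (protocol 8.3 and SAP 4.3, Part H): 300 evaluable on mRNA-1273.222 and 260 on mRNA-1273; two-sided alpha 0.05; true GMR 1.5 for BA.4/5 and 1.0 for D614G; SD of log titer 1.5, taken as natural log; GMR margin 1.5; true SRR 95% in both arms for both strains; stated power about 60%.

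**1. Reproducing the stated power at 5%.**

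- GMR standard error: 1.5 × √(1/300 + 1/260) = 0.1271, and ln 1.5 = 0.4055.
- BA.4/5 GMR non-inferiority: Φ(2 × 0.4055/0.1271 − 1.96) > 0.999.
- D614G GMR non-inferiority: Φ(0.4055/0.1271 − 1.96) = 0.891.
- BA.4/5 GMR superiority: the same expression, 0.891. Passing it implies BA.4/5 GMR non-inferiority.
- SRR standard error: √(0.95 × 0.05 × (1/300 + 1/260)) = 0.01847.
- BA.4/5 SRR at 5%: Φ(0.05/0.01847 − 1.96) = 0.773. Exact enumeration of the unstratified Miettinen-Nurminen (MN) test gives 0.749.
- SRR at 10%: Φ(0.10/0.01847 − 1.96) = 0.9997 (MN 0.9994).

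Multiplying as if the tests were independent:

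| Set of hypotheses | BA.4/5 SRR margin 5% | Margin 10% |
|---|---|---|
| All five, with superiority | 0.613 (MN 0.594) | 0.793 (MN 0.792) |
| Four non-inferiority criteria | 0.688 (MN 0.667) | 0.890 (MN 0.890) |

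The stated 60% matches all five hypotheses at 5%. The same convention, with superiority included, gives 89.6% for Part F (stated 89%) and 71.1% for Part G (stated 71%), which supports this reading of how the figure was obtained.

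**2. Where the verdicts split.** Unstratified MN lower limits against 247/260 control responders (95%):

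| Responders on mRNA-1273.222 | Lower limit | Protocol | SAP |
|---|---|---|---|
| 282/300 | −4.91% | pass | pass |
| 281/300 | −5.30% | fail | pass |
| 276/300 (92%) | −7.22% | fail | pass |
| 269/300 | −9.87% | fail | pass |
| 268/300 | −10.24% | fail | fail |

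**3. Chance of passing the SRR criterion taken alone** (exact MN, true control rate 95%):

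| True rate on mRNA-1273.222 | 5% rule | SAP rule |
|---|---|---|
| 95% | 74.9% | 99.9% |
| 92% | 15.0% | 90.1% |
| 90% | 2.4% | 59.5% |
| 85% | <0.1% | 2.4% |

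At the planned rates, the extra branch decides 99.9 − 74.9 = 25% of trials. The last row shows that the SAP rule controls error at a 10% margin; what has changed is the margin.

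**The case against.** The strongest objection is that SRR is never judged alone. The objective also needs BA.4/5 GMR non-inferiority, and both are computed from the same titers. Suppose titers are lognormal with SD 1.5 in both arms and seroresponse is a fixed threshold that 95% of controls exceed. A true SRR of 90% then implies a GMR of about 0.58, and both BA.4/5 criteria are met together in about 0.1% of trials or fewer under either rule. At 92% (GMR about 0.70) the joint figures are about 3% and 5–6%. At the planned GMR of 1.5 the implied SRR is about 97%, and superiority together with SRR passes in 88.4% versus 88.9% of trials. This stands as a limit on practical impact: the deficit rows in the last table must be read as the SRR criterion only. It does not remove the difference. At GMR 1.0 with 95% in both arms, the joint figures under this model are about 70% and 89%. The model is also an assumption outside the documents, whose own planning pairs GMR 1.5 with equal SRRs.

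A second objection is that the SAP change table proves little. Version 5.0 introduced Part H as a whole and logged it as "Added details for Part H", so a tier written then would need no separate entry. That is fair. Silence does not date the tier. But the same entry says it follows Amendment 9, which contains no 10% tier for BA.4/5.

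A third objection is that SAP Table 3 lists Part H Day 29 BA.4/5 as already tested, so deleting a tier now is also a late change. Deletion, however, restores the rule in the governing amendment and in the power statement, whereas raising the protocol margin would relax a primary criterion. Table 3 lists only D614G and BA.1 for the Part F comparator, so it does not show that the comparison was run.

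**Conclusion.** The conflict is real, lies in the current text of both documents, and must be fixed. The protocol requires a lower limit above −5% for BA.4/5 SRR; the SAP accepts any limit above −10% for the primary objective and for opening superiority. At the planned sizes and 247/260 control responders, this is the gap between needing 282 and needing 269 of 300 responders. At 95% in both arms it moves the SRR pass probability from 75% to 99.9%, and power for all five hypotheses from 59–61% to 79%.

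The power figures assume independent tests, as the plan's own figure appears to. The MN figures are unstratified, because the SAP stratifies by age group but gives no stratum sizes. The testing-strategy figures were not available to check. The protocol writes the −5% bound and the superiority gate explicitly only in the synopsis; its body gives the 5% margin. The documents do not show when the 10% tier was written or whether a result has been reported under it.

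**What to change.** In SAP 4.2 and 6.4.3:

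- Remove the branch for limits above −10% but not above −5% from the success rule. State that BA.4/5 SRR non-inferiority is met only if the lower 95% limit is above −5%.
- In the superiority gate, replace the single 10% margin with 5% for BA.4/5 and 10% for ancestral D614G.
- Label any statement comparing the BA.4/5 limit with −10% as descriptive.
- Record the change in the SAP change table.

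The protocol should not be amended to 10% unless dated documentation shows that the tiered rule was set before the Day 29 data were available.

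The cost is SAP wording and one table entry. If a Day 29 result has already been reported under the tiered rule, that statement needs relabelling. The chance of success stays where the plan already puts it: about 60% for all five hypotheses, or 67–69% for the four non-inferiority criteria.
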